- Frequency distribution (number & percent) of failure for Pelvi- abdominal infection. Chi² test will be used to determine *p*-value and significance between the 2 groups.
- Frequency distribution (number & percent) of relapse for Pelvi- abdominal infection. Chi² test will be used to determine *p*-value and significance between the 2 groups.

B. Days for complete healing of post-operative wounds after 8 days of treatment (Follow up 1 visit) & 15 days of treatment (Follow up 2 visit or End of study visit)

Descriptive analysis (mean, Standard Deviation, Median, Interquartile Range, Minimum and Maximum) of days for complete healing versus combined treatment will be after 8 days of treatment (Follow-up 1 V) & 15 days of treatment (End of study visit). Percent change will be calculated between baseline to End of study. Paired t-test will be used to determine *p*-value and significance between baseline and at the end of the study. Unpaired t-test will be used to determine the *p*-value and significance between Changes in complete healing between 2 groups.

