12.2 Patient Enrollment

After signing the informed consent form, each potential subject will be screened for eligibility based on the inclusion and exclusion criteria specified. Randomization will be done.

All visits will occur as closely as possible to the scheduled visit dates with window of 3 days. In case of a premature discontinuation of the study, the subject, will be, if possible called in for a last visit. Even if the subject would not be able to attend, the 'End of Study' forms will be completed .

12.3 12.3 Schedule of visits

Table 1: Schedule of Visits

Observation	Visit 1 (Screening & treatment)	(Follow-up 1 V)	(Follow-up 2 V) End of Study
Time lines	Day 0	Day 8	Day 15
Informed consent document signed	X		
Review Inclusion/Exclusion criteria	X		
Patient Demographics	X		
Significant medical history and current disease status	X		
Physical examination	X	X	X
Vital Signs	X	X	X
Child-Pugh Score	X		
Concomitant medications	X	X	X
Safety Laboratory Tests:			
FBS	X		
Total Leucocytic count	X		X
SGOT (ALT)	X		X
SGPT (AST)	X		X
Total Bilirubin	X		X
S. Creatinine	X		X
Serum β -HCG: (for females in childbearing period)	X		
Pelvi-abdominal Ultrasound & others (Optional)	X		X
Study Drug Dispensed	X	X	
Drug Accountability		X	X

Observation	Visit 1 (Screening & treatment)	(Follow-up 1 V)	(Follow-up 2 V) End of Study
Time lines	Day 0	Day 8	Day 15
Presence of any signs/symptoms of post-operative wound infection such as redness, fever or wound discharge. (in case of post-operative subjects)	X	X	X
Days for complete healing		X	X
Complete resolution, improvement, failure or relapse of pelvi - abdominal infection		X	X
AE		X	X
SAE		X	X
Study Completion Form			X

The subsequent visits will occur as follows :

- **Visit 1 (Screening & treatment initiation Visit):** Day 0
- **Follow-up V1:** Day 8 (+/-) 3 days
- **Follow-up V2 & End of Study Visit:** Day 15 (+/-) 3 days

12.3.1 Visit 1 (Screening & treatment initiation):

- During this visit, subjects will be informed about the study. If they are willing to participate in the study, they will sign the written ICF. A copy of the signed ICF will be given to the subject. In addition, the subjects will be evaluated for study eligibility according to the inclusion and exclusion criteria.
- Screening Assessments will include: physical examination, vital signs, demographic data (Age & Gender), medical history and concomitant medications.

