12.3.2 Follow-up 1 Visit (Day 8)

It could be the end of treatment for some subjects.

The following procedures will be done this visit, and all relevant information will be recorded in the source document and forms:

- Subjects will undergo thorough general physical examination and Vital signs
- Presence of any signs/symptoms of post-operative wound infection such as redness, fever or wound discharge will be recorded (in case of post-operative subjects)
- Any changes in concomitant medication, illness and treatment will be recorded.
- Checking if any AE or SAEs happened and recording them in their separate forms.
- Days for complete healing will be checked, if happened.
- Complete resolution, improvement, failure or, relapse of Pelvi- abdominal infection will be recorded
- Subjects will be asked to come after 15 days of the treatment (Day 15) for follow up, with window of 3 days
- In case of any premature discontinuation of the study, the subject will be, if possible, called in for a last visit. Even if the subject was not able to attend the last visit, the End of Study Form must be completed.
- In case of complete resolution, end of the study lab testing will be asked and recorded and End of the study Form will be completed

12.3.3 Follow-up 2 Visit & End of Study Visit (Day 15):

It is the end of study visit for subjects.

The following procedures will be done during this visit, and all relevant information will be recorded in the source document and forms:

- Subjects will undergo thorough general physical examination and Vital signs
- Presence of any signs/symptoms of post-operative wound infection such as redness, fever or wound discharge will be recorded (in case of post-operative subjects)
- Any changes in concomitant medication, illness and treatment will be recorded.
- Checking if any AE or SAEs happened and recording them in their separate forms. Days for complete healing will be checked.
- Complete resolution, improvement, failure or, relapse of Pelvi- abdominal infection will be recorded
- Lab results will be checked for: S. Creatinine, Total leukocytes count, Liver enzymes (SGOT, SGPT), and total bilirubin
- Pelvi-abdominal Ultrasound and others will be done, if needed.
- The End of Study Form must be completed.

13 Management & Reporting of Adverse Events

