- Frequency distribution (number & percent) of presence of any signs/symptoms of post-operative wound infection such as redness, fever or wound discharge. Chi² test will be used to determine *p*-value and significance between the 2 groups.

B. Change in Total leukocytes count between baseline (visit 1) to End of study visit

- Descriptive analysis (mean, Standard Deviation, Median, Interquartile Range, Minimum and Maximum) of total leucocyte will be from baseline (visit 1) to End of study visit. Percent change will be calculated between baseline to End of study. Paired t-test will be used to determine p-value and significance between baseline and at the end of the study. Unpaired t-test will be used to determine the p-value and significance between Changes in total leucocyte between 2 groups.

C. Change in Liver enzymes (SGOT) between baseline (visit 1) to End of study visit

- Descriptive analysis (mean, Standard Deviation, Median, Interquartile Range, Minimum and Maximum) of Liver enzymes (SGOT) will be from baseline (visit 1) to End of study visit. Percent change will be calculated between baseline to End of study. Paired t-test will be used to determine p-value and significance between baseline and at the end of the study. Unpaired t-test will be used to determine the p-value and significance between Changes in Liver enzymes (SGOT) between 2 groups.

D. Change in Liver enzymes (SGPT) between baseline (visit 1) to End of study visit

- Descriptive analysis (mean, Standard Deviation, Median, Interquartile Range, Minimum and Maximum) of Liver enzymes (SGPT) will be from baseline (visit 1) to End of study visit. Percent change will be calculated between baselines to End of study. Paired t-test will be used to determine p-value and significance between baseline and at the end of the study. Unpaired t-test will be used to determine the p-value and significance between Changes in Liver enzymes (SGPT) between 2 groups.

8.9 Secondary Efficacy analysis:

A. Complete resolution, improvement, failure or relapse of Pelvi- abdominal infection

- Frequency distribution (number & percent) of complete resolution, improvement, failure or relapse for Pelvi- abdominal infection. Chi² test will be used to determine p-value and significance between the 2 groups.
- Frequency distribution (number & percent) of improvement for Pelvi- abdominal infection. Chi² test will be used to determine p-value and significance between the 2 groups.

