- Frequency distribution (number & percent) of failure for Pelvi- abdominal infection. Chi² test will be used to determine p-value and significance between the 2 groups.

- Frequency distribution (number & percent) of relapse for Pelvi- abdominal infection. Chi² test will be used to determine p-value and significance between the 2 groups.

B. Days for complete healing of post-operative wounds after 8 days of treatment (Follow up 1 visit) & 15 days of treatment (Follow up 2 visit or End of study visit)

- Descriptive analysis (mean, Standard Deviation, Median, Interquartile Range, Minimum and Maximum) of days for complete healing versus combined treatment will be after 8 days of treatment (Follow-up 1 V) & 15 days of treatment (End of study visit). Percent change will be calculated between baseline to End of study. Paired t-test will be used to determine p-value and significance between baseline and at the end of the study. Unpaired t-test will be used to determine the p-value and significance between Changes in complete healing between 2 groups.

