9.4.2 Primary Efficacy

Table 9 *Number and percent of complete resolution for pelvi- abdominal infection among treatment groups*

	Group A (N=156)	Group B (N=156)	p-value
No of complete resolution for pelvi-abdominal infection, N (%)			
No of incomplete resolution for pelvi-abdominal infection, N (%)			

Table 10 *Number and percent of complete healing of the post-operative wounds among treatment groups*

	Group A (N=156)	Group B (N=156)	p-value
Complete healing, N (%)			
Incomplete healing, N (%)			
No healing, N (%)			

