9.5 Secondary End Point

9.5.1 Secondary Safety:

Table 11 *Number and percent of signs/symptoms of post-operative wound infection among treatment groups*

	Group A (N=156)	Group B (N=156)	p-value
No of signs/symptoms of post-operative wound infection, N (%)			
Redness, N (%)			
Fever, N (%)			
Wound discharge, N (%)			

Table 12 *Percent Change in mean Total leukocytes among treatment groups*

	Group A (N=156)	Group B (N=156)	p-value
Visit 1, mean ± SD			
End of study visit, mean ± SD			
% Change			
p-value between V1 & End of study visit			
p-value between 2 groups			

Table 13 *Percent Change in mean SGOT among treatment groups*

	Group A (N=156)	Group B (N=156)	p-value
Visit 1, mean ± SD			
End of study visit, mean ± SD			
% Change			
p-value between V1 & End of study visit			
p-value between 2 groups			

Table 14 *Percent Change in mean SGPT among treatment groups*

	Group A (N=156)	Group B (N=156)	p-value
Visit 1, mean ± SD			
End of study visit, mean ± SD			
% Change			
p-value between V1 & End of study visit			
p-value between 2 groups			

9.5.2 Secondary Efficacy:

Table 15 Number and percent of complete resolution, improvement, failure or relapse for Pelvi- abdominal infection among treatment groups

	Group A (N=156)	Group B (N=156)	p-value
Complete resolution, N (%)			
Improvement, N (%)			
Failure or relapse, N (%)			

Table 16 *Percent Change in mean days for complete healing of post-operative wounds after 8 days of treatment (Follow up 1 visit) among treatment groups*

	Group A (N=156)	Group B (N=156)	p-value
Visit 1, mean ± SD			
Follow up 1 visit, mean ± SD			
% Change			
p-value between V1 & Follow up 1 visit			
p-value between 2 groups			

Table 17 *Percent Change in mean days for complete healing of post-operative wounds after 15 days of treatment (Follow up 2 visit or End of study visit) among treatment groups*

	Group A (N=156)	Group B (N=156)	p-value
Visit 1, mean ± SD			
Follow up 2 visit, mean ± SD			
% Change			
p-value between V1 & Follow up 2 visit			
p-value between 2 groups			

10 Reference:

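### Days to complete wound healing is analysed as a change from a baseline that does not exist, and unhealed wounds have no value or censoring rule

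*SAP*

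**What the plan says.** SAP 8.9 B, repeated in protocol 10.7.9 B, describes days to complete healing by mean, SD, median and range at Day 8 and Day 15. It then adds "Percent change will be calculated between baseline to End of study", a paired t-test of baseline against end of study, and for the groups: "Unpaired t-test will be used to determine the p-value and significance between Changes in complete healing between 2 groups".

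The table shells carry this through. Table 16 is titled "Percent Change in mean days for complete healing of post-operative wounds after 8 days of treatment (Follow up 1 visit) among treatment groups" and has a Visit 1 mean and SD row, a % Change row and a row labelled "p-value between V1 & Follow up 1 visit". Table 17 repeats the layout for Follow-up 2.

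Table 1 of the protocol (12.3, Schedule of visits) marks "Days for complete healing" at Day 8 and Day 15 only. At Day 8 (protocol 12.3.2) the instruction is: "Days for complete healing will be checked, if happened". Both follow-up visits have a window of 3 days either way.

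The primary efficacy analysis (SAP 8.7 B) provides for wounds that do not heal. Table 10 has the row "Incomplete healing, N" and a further row for no healing.

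**The concern.** There are two separate problems.

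- **No baseline.** The text follows the laboratory wording of SAP 8.8 B to D, for example "Unpaired t-test will be used to determine the p-value and significance between Changes in total leucocyte between 2 groups". A leukocyte count is measured at Visit 1, so change from baseline is defined there. A healing time is a single duration and is not measured at Visit 1.
- **No rule for unhealed wounds.** A patient unhealed at the visit has no number of days. With no stated value, imputation or censoring rule, the natural default is to average those who healed. That group is selected by outcome: the arm that heals more slowly drops its slowest patients, which shrinks a real difference.

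At stake is whether this secondary endpoint can be reported and interpreted. If the final SAP repeats the text, the analysis actually used would have to be settled later, in an open-label trial.

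**Working it through.** The plan states no figure for this endpoint (no healing rate, expected difference or number of post-operative patients), so there is nothing to reproduce. The first two steps need no assumption. The third is an illustration.

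**1. The baseline rows.** Let D be a patient's days to healing. No Visit 1 value exists, so the Visit 1 mean, the percent change and the paired test have no input. Suppose 0 is entered at Visit 1:

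- Percent change = 100 × (D − 0)/0, which is undefined.
- The paired test asks whether mean D exceeds 0, which is true by construction.
- Change = D − 0 = D, so the unpaired test of changes becomes a test of the days themselves.

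Only the follow-up mean row and the between-group comparison can carry information, and only for patients with a value of D.

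**2. Unhealed wounds.** Table 10 expects them, and Day 8 records days only where healing has occurred. No section of either document gives the others a value, a censoring time or a time-to-event method. The per-protocol restriction (SAP 8.1) does not close the gap, because a patient can complete the study unhealed. The time origin (for example surgery or first oral dose) is not stated. Tables 16 and 17 are headed N=156 per group, although non-operative patients have no wound.

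**3. Possible size.** Assumptions not in the documents: 78 post-operative patients per arm (half of 156); Weibull healing times with shape 2, rounded up to whole days; medians m = 10, 7 or 5 days in the faster arm and 1.3 m in the slower; visits exactly on Days 8 and 15; full follow-up; two-sided 5%; 2000 to 3000 simulated trials per scenario.

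Proportion healed by day t = 1 − 2^(−(t/m)²). For m = 10 and t = 15 this is 1 − 2^(−2.25) = 79%. For m = 13 it is 1 − 2^(−1.33) = 60%. The true mean is 1.0645 m, so the true differences are 1.0645 × 3, 2.1 and 1.5 = 3.2, 2.2 and 1.6 days.

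Day 15 (Table 17):

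| Medians | Healed by Day 15 | Healed-only means | Healed-only t-test | Visit-based log-rank | Exact-day log-rank |
|---|---|---|---|---|---|
| 10 vs 13 | 79% vs 60% | 8.9 vs 9.6 | 14% | 76% | 78% |
| 7 vs 9.1 | 96% vs 85% | 7.5 vs 8.6 | 46% | 81% | 88% |
| 5 vs 6.5 | nearly all | 5.8 vs 7.2 | 79% | 79% | 90% |

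Day 8 (Table 16):

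| Medians | Healed by Day 8 | Healed-only difference (days) | Healed-only t-test | Slower arm's mean equal or shorter |
|---|---|---|---|---|
| 10 vs 13 | 36% vs 23% | 0.1 | 6% | 44% of trials |
| 7 vs 9.1 | 60% vs 41% | 0.2 | 7% | 31% of trials |
| 5 vs 6.5 | 83% vs 65% | 0.4 | 16% | 15% of trials |

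With smaller effects the Day 15 figures, in the same scenario order, are:

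- Ratio 1.2: healed-only 10%, 29%, 51%; visit-based log-rank 45%, 50%, 48%.
- Ratio 1.1: healed-only 7%, 12%, 18%; visit-based log-rank 17%, 19%, 16%. Neither is adequate.

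With no true difference, the Day 15 methods reject in 4.5% to 6.0% of trials, so no inflation of type I error was found.

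**The case against.** The strongest reply is that the signal lost here is non-healing, and the plan already tests that as a primary endpoint. Under the same assumptions at ratio 1.3, a chi-squared test on the proportion healed by Day 15 rejects in 72%, 69% and 11% of trials. Counting a rejection by either that test or the healed-only t-test gives 78%, 84% and 82%, close to the visit-based log-rank. This pairs two unadjusted 5% tests and assumes Table 10 uses status by Day 15. The point stands: the trial as a whole loses little ability to detect a difference. It does not make the secondary analysis valid as written.

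Other objections also have weight:

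- Every size input is assumed, and healed-only analysis is an inference from the missing rule. The figures show direction only.
- The choice of method is partly preference. When nearly all wounds heal, the visit-based log-rank is level with or slightly below the healed-only t-test (48% against 51% at ratio 1.2). At ratio 1.3 a t-test with a fixed value of 16 days for unhealed wounds reaches 69%, 82% and 87%, above the visit-based log-rank in two of three scenarios.
- The efficacy set is per protocol, so withdrawn patients stay excluded whatever rule is adopted. Protocol 12.3.2 also closes the study at Day 8 on complete resolution. If that applied to a patient with an open wound, censoring could depend on outcome. These are separate matters.
- SAP 8.2 calls for a final SAP before database lock with differences documented, so a late choice is not certain. That document is the place for the correction.

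**Conclusion.** The concern holds. That three rows in each of Tables 16 and 17 have no meaning, and that unhealed wounds have no rule, follows from the documents without any assumption. Confidence in that is high.

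Confidence in the size is low. It depends on how many patients are post-operative, how many wounds are unhealed at each visit, and whether healed-only analysis is what would be done. The loss is large when many wounds are unhealed, greatest in Table 16, and small at Day 15 when nearly all heal.

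The point concerns one secondary endpoint. It does not make the primary proportion-healed result wrong. The analysis should be corrected because it is wrong as written, not merely short of detail.

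**What to change.** In the final SAP, before database lock, revise SAP 8.9 B and Tables 16 and 17, and record the difference from protocol 10.7.9 B:

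1. Delete the Visit 1, percent-change and paired-test text and rows for this endpoint.
2. Define day 0 for the count of days, for example treatment start.
3. Compare the groups on time to complete healing, with unhealed wounds kept and censored at their last assessment (Kaplan-Meier and log-rank). If the CRF does not hold the exact healing day, use a visit-based or interval-censored version with actual visit dates, because of the 3-day windows. Another pre-stated rule that keeps unhealed wounds, such as a fixed late value, would also remove the selection.
4. Report the number of post-operative patients analysed in each group, and the numbers healed by Day 8 and by Day 15, in place of N=156.

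The cost is two paragraphs and two table shells. The visit-based version needs no new data. The exact-day version needs a healing date on the CRF, which should be confirmed.

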8.10 Interim analysis

Optional

9 Results:

9.1 Demographic Data and Vital Signs

9.2 Medical history

9.3 Concomitant Medication

9.4 Primary End Point:

9.4.1 Primary Safety

9.4.1 Primary Efficacy

9.5 Secondary End Point:

9.5.1 Secondary Safety

9.5.1 Secondary Efficacy

9.1 Demographic Data and vital signs

Table 1 Demographic Data and vital signs among treatment Groups

	Group A (N=156)	Group B (N=156)	p-value
Gender (male), N (%)			
Age (Yrs.), mean (SD)			
BMI, mean (SD)			
Pulse, mean (SD)			
Systolic, mean (SD)			
Diastolic, mean (SD)			

9.2 Medical History

Table 2 Number and percent of medical history among treatment groups

	Group A (N=156)	Group B (N=156)	p-value
Med history 1, N (%)			
Med history 2, N (%)			
Med history 3, N (%)			

9.3 Concomitant Medication

Table 3 Number and percent of Concomitant medication among treatment groups

	Group A (N=156)	Group B (N=156)	p-value
N			
ConMed1, N (%)			
ConMed2, N (%)			
ConMed3, N (%)			

9.4 Primary End Point

9.4.1 Primary Safety

Table 4 *Number and percent of Adverse Event necessitating a change or discontinuation of treatment among treatment groups*

	Group A (N=156)	Group B (N=156)	p-value
Total No of SAE, N (%)			
SAE1, N (%)			
SAE2, N (%)			
SAE3, N (%)			

Table 5 *Number and percent of Serious Adverse Event among treatment groups*

	Group A (N=156)	Group B (N=156)	p-value
Total No of SAE, N (%)			
SAE1, N (%)			
SAE2, N (%)			
SAE3, N (%)			

Table 6 *Number and percent of causes of treatment discontinuations among treatment groups*

	Group A (N=156)	Group B (N=156)	p-value
Total No of treatment discontinuations, N (%)			
Cause1, N (%)			
Cause2, N (%)			
Cause3, N (%)			

Table 7 *Number and percent of Adverse Event necessitating a change or discontinuation of treatment among treatment groups*

	Group A (N=156)	Group B (N=156)	p-value
Total No of AE, N (%)			
AE1, N (%)			
AE2, N (%)			
AE3, N (%)			

Table 8 *Number and percent of Adverse Event among treatment groups*

	Group A (N=156)	Group B (N=156)	p-value
Total No of AE, N (%)			
AE1, N (%)			
AE2, N (%)			
AE3, N (%)			

9.4.2 Primary Efficacy

Table 9 *Number and percent of complete resolution for pelvi- abdominal infection among treatment groups*

	Group A (N=156)	Group B (N=156)	p-value
No of complete resolution for pelvi-abdominal infection, N (%)			
No of incomplete resolution for pelvi-abdominal infection, N (%)			

Table 10 *Number and percent of complete healing of the post-operative wounds among treatment groups*

	Group A (N=156)	Group B (N=156)	p-value
Complete healing, N (%)			
Incomplete healing, N (%)			
No healing, N (%)			

9.5 Secondary End Point

9.5.1 Secondary Safety:

Table 11 *Number and percent of signs/symptoms of post-operative wound infection among treatment groups*

	Group A (N=156)	Group B (N=156)	p-value
No of signs/symptoms of post-operative wound infection, N (%)			
Redness, N (%)			
Fever, N (%)			
Wound discharge, N (%)			

Table 12 *Percent Change in mean Total leukocytes among treatment groups*

	Group A (N=156)	Group B (N=156)	p-value
Visit 1, mean ± SD			
End of study visit, mean ± SD			
% Change			
p-value between V1 & End of study visit			
p-value between 2 groups			

Table 13 *Percent Change in mean SGOT among treatment groups*

	Group A (N=156)	Group B (N=156)	p-value
Visit 1, mean ± SD			
End of study visit, mean ± SD			
% Change			
p-value between V1 & End of study visit			
p-value between 2 groups			

Table 14 *Percent Change in mean SGPT among treatment groups*

	Group A (N=156)	Group B (N=156)	p-value
Visit 1, mean ± SD			
End of study visit, mean ± SD			
% Change			
p-value between V1 & End of study visit			
p-value between 2 groups			

9.5.2 Secondary Efficacy:

Table 15 Number and percent of complete resolution, improvement, failure or relapse for Pelvi- abdominal infection among treatment groups

	Group A (N=156)	Group B (N=156)	p-value
Complete resolution, N (%)			
Improvement, N (%)			
Failure or relapse, N (%)			

Table 16 *Percent Change in mean days for complete healing of post-operative wounds after 8 days of treatment (Follow up 1 visit) among treatment groups*

	Group A (N=156)	Group B (N=156)	p-value
Visit 1, mean ± SD			
Follow up 1 visit, mean ± SD			
% Change			
p-value between V1 & Follow up 1 visit			
p-value between 2 groups			

Table 17 *Percent Change in mean days for complete healing of post-operative wounds after 15 days of treatment (Follow up 2 visit or End of study visit) among treatment groups*

	Group A (N=156)	Group B (N=156)	p-value
Visit 1, mean ± SD			
Follow up 2 visit, mean ± SD			
% Change			
p-value between V1 & Follow up 2 visit			
p-value between 2 groups			

10 Reference:

